### **10.1.2 Advanced stage HD**

**BACKGROUND:** The UHDRS does not allow a meaningful assessment for the advanced stages of HD for a number of reasons. For example, the standard UHDRS cognitive assessment consisting of timed psychomotor tasks, cannot be administered to people in more advanced stages of HD due to their motor impairment and dysarthria. Therefore, an important component of the cognitive phenotype is very often not assessed in the advanced stage HD participants. Likewise, communication impairments preclude an interview-based behavioural assessment. Lastly, the motor phenotype for all items of the motor scale, requiring active participation by the participant is not informative in more advanced stages. Other aspects like impaired mobility and control over bodily functions that contribute greatly to the caregiver burden and the medical needs of advanced stages of HD are not captured in the standard UHDRS assessment. Therefore this sub-study proposes an assessment of advanced stage HD based on the pioneering scale development lead by the sub-study team.

**AIM:** To validate a novel scale called “Advanced-stage UHDRS” for use in clinical and research practices.

**STUDY POPULATION:** Enroll-HD participants with a Total Functional Capacity score of  $\leq 5$  (includes Stage III) and a reduced independence scale score of  $< 70\%$  .

**ASSESSMENT:** The Advanced-HD scale consists of four components: motor function, somatic domain, cognitive assessment and behavioural assessment.

**ASSESSMENT DURATION:** 30 minutes

**METHODOLOGICAL APPROACH:** Trained raters will administer the Advanced-HD scale in addition to the standard UHDRS. Participants will be selected based on TFC score of  $\leq 5$ . The population sample will be stratified according to each scale point on the TFC from 0 to 5. The study aims to recruit a total of 120 advanced stage HD patients. Participants undergo at least two assessments at 1 year interval ( $\pm 2$ months). The Advanced-HD scale will be assessed with the standard UHDRS. The first phase of this study will be coordinated in three countries.

**OUTCOMES:** The objective is to determine whether the Advanced-HD scale is useful at each of the TFC scores below or equal to 5. The main objective is to compare the

capacity of both Advanced-HD scale and standard UHDRS to assess the progression of the disease at one year. Once the Advanced-HD scale has been validated and, if necessary, the inclusion criteria have been refined, a second phase will assess the performance of the Advanced-HD scale between languages.

### **10.1.3 Juvenile-onset HD**

**BACKGROUND:** In approximately 5% of cases, the onset of symptoms may occur before the age of 20 years, and this is called Juvenile-onset HD (JD). The clinical presentation of JD can be strikingly different from that of adult-onset HD. In young people affected by JD, and particularly in those with onset in the first decade, there is a dominant clinical picture of bradykinesia, rigidity and dystonia. They are also more likely to develop epilepsy. This distinct JD phenotype is not captured completely by the items of the current version of UHDRS, which was originally developed to assess the most prevalent phenotype which is the adult onset of the disease. Therefore, for patients with Juvenile HD, a modified version of the motor section of the UHDRS will be used alongside the existing motor section so that new items which may be more appropriate to the clinical presentation seen in JD can be evaluated. To ensure that a complete picture of the neurological symptoms of JD is gained, a standard full neurological examination appropriate to age will be carried out and recorded. In addition, parent/guardians of those affected by JD will be invited to record symptoms and details of any symptomatic treatments being used in a diary. This additional information will allow us to observe the progression of symptoms in JD and also allow us to gain a better understanding of the usefulness of different treatments in managing these symptoms.

#### **AIMS:**

- a. To assess the reliability and validity of the JD assessment to track the onset and progression of this rare phenotype. To construct new rating scales based on an iterative process.
- b. To monitor the progression of symptoms and signs of those affected by JD using modified UHDRS scales of motor and function (functional assessment, TFC). This will provide some basic data to analyse the usefulness of the proposed rating scales.
- c. Caregivers of those affected by JD will be invited to record both symptoms experienced by the person with JD and details of any symptomatic treatment being used in a diary. This will allow us to observe the progression of symptoms in JHD and also allow us to gain a better understanding of the usefulness of different treatments in managing these symptoms.
- d. There may be significant delays in diagnosis especially if the young person presents with behavioural problems. Caregivers will be asked questions to capture the

number of contacts with professionals in the time between onset of concerns about the young person and the confirmation of diagnosis.

- e. To undertake a qualitative study of the issues experienced by young people and caregivers in order to develop new rating scales which assess relevant aspects of the phenotype. Not all aspects can be undertaken but in depth interviews will take place if pain is a specific feature of the condition for an individual.

**STUDY POPULATION:** Enroll-HD participants with JD (motor onset aged 20 or younger).

**ASSESSMENT:**

- a. UHDRS JD Motor Assessment
- b. UHDRS JD Functional Assessment (including JD functional scale and JD total functional capacity scale)
- c. Diagnosis questions (brief questionnaire relating to the process of diagnosis). This data will only be collected at the first baseline visit.
- d. Standard full neurological examination appropriate to the age of the individual being assessed will also be carried out to identify any other possible signs of JD.
- e. Diary to help caregivers monitor medication and symptoms on an ongoing basis.
- f. Two-three patients who are willing will be invited to participate in a video of the motor examination to facilitate consistency of data capture as part of a wider international collaboration.
- g. Five in depth taped interviews will be undertaken to explore carers perception of pain. The interviews will be semi-structured and undertaken by a psychologist with experience of qualitative work and analysed using Interpretative Phenomenological Analysis. The aim is to inform the development of questions about pain as feature of JD and builds on a previous collaboration (1).

**ASSESSMENT DURATION:** 45 minutes. Diary entries (paper based or online) would be completed whenever symptoms and changes to medication were noted by the caregiver.

**METHODOLOGICAL APPROACH:** Some patients with JD are already being seen as part of the Enroll-HD project and so the additional data can be accommodated as part of the Enroll-HD study visit. Other patients may not attend the clinics but families identified from paediatric neurologists or the patients' organizations will be given the option of being seen at home by the research assistant who will be trained in the following assessments. Data will be collected and analysed after 6 months to ensure that no further changes need to be made to the diary format / instructions.

OUTCOMES: Data will be collected from 30 JD patients and subjected to a Rasch analysis which will give a guide to the performance of the rating scales and aid further refinement. N = 30 has been determined from both empirical and simulation Rasch analysis studies as the minimum number required to produce useful items to move forward to larger more definitive studies.

Historically, scale development and evaluation involved large samples of people. These are costly, time consuming and, in the case of JD, not easy. Rasch analysis lends itself to smaller sample work for two reasons. First, an inherent mathematical feature of the model is parameter separation. That is, the estimates of item parameters are independent of the sampling distribution of the persons. Likewise the estimates of person parameters are independent of the sampling distribution of the items.

Methodology for statistical analysis will follow Rasch analysis using statistical package RUMM2020. The parameterization is maximum likelihood method.

Basic analyses undertaken within the Rasch measurement framework include, but are not limited to, an examination of:

- a. targeting of person measurements to item threshold locations
- b. ordering of category threshold locations, and category probability curves
- c. threshold probability curves
- d. threshold map
- e. distribution and ordering of item locations
- f. statistical (overall chi sq, item fit residuals, item chi square probability) and graphical (item characteristic curves) fit indicators
- g. residual correlations
- h. differential item functioning
- i. scale information function
- j. person separation index
- k. person fit
- l. relationship between raw scores and interval measurements

#### **10.1.4 Frontal behaviours (FrSBe, Irritability and Apathy)**

**BACKGROUND:** Standard clinical assessments used to capture neuropsychiatric features of HD (the UHDRS Behaviour and Problem Behaviour Assessment-Short) are interview-based rating scales conducted by a trained rater with the patient, and when available, the companion/caregiver. These assessments provide an overall impression of the frequency and severity of key neuropsychiatric problems over a period of 4 weeks prior to the interview. Whilst these rating scales are sufficient in identifying a clinical problem, there is a clear need to identify robust clinical outcome measures of *specific* psychiatric features to inform clinical practice and provide a reference point for future trials of new treatments as they are developed. This sub-study proposes to test the suitability of existing measures of frontal behaviours, in particular apathy and irritability, to a large HD population in order to derive appropriate sub-scales that can be used in clinical intervention. These preliminary data are required to inform power calculations for future clinical trials aimed at modifying symptom frequency and severity.

#### **AIMS:**

##### **Primary aims:**

- a. To determine the reliability and validity of frontal behaviour measures, both patient, informant and rater versions
- b. To investigate the differences in patient and informant based assessment methods
- c. To better understand frontal-type behaviours in HD

##### **Secondary aims**

- a. To investigate the association between the outcome measures and various demographic and clinical characteristics
- b. To investigate the association between the outcome measures and the other neuropsychiatric scales (e.g. PBA-s, UHDRS behaviour, HADS-SIS)

**STUDY POPULATION:** Confirmed HD gene mutation carriers (Pre-HD, Stages I to III), aged 18 years and older

#### **ASSESSMENT BATTERY:**

- a. Irritability component of Apathy and Irritability Scale (2); patient, informant and rater versions
- b. Irritability Scale for HD (ISHD); Companion diary entries, once per day for 7 consecutive days
- c. Apathy Scale; patient, informant and rater versions.

- d. Frontal Systems Behaviour Scale (FrSBe; participant and informant versions)

ASSESSMENT DURATION: 45 minutes each for patient and companion. 20 minutes for rater.

METHODOLOGICAL APPROACH: The first phase will coordinate study sites across three countries. An estimated 300 participants recruited from different stages of the disease will be enrolled into the study (100 participants in total per country; 50 Pre-HD, 25 Stage I, 25 Stage II and 25 Stage III).

For rater-based questionnaires, a small pilot design will be used to determine a learning effect for raters who are new to these scales. Comparisons will be run using first 10 participants per study site.

Test-retest reliability will require approximately 170 participants across languages, with a follow-up assessment after 14 days (+/- 7 days). For the Irritability Scale (HD), which follows a 7-day diary format, test-retest reliability will take diary entries completed over 14 consecutive days. Comparisons will be made between entries recorded in week 1 compared to week 2.

For rater based versions of scales, it will be important to assess inter-rater reliability (n=25 per language area). Two raters should complete ratings at the same time during the clinical interview. If it is not possible to have a second rater present during the interview, then videoed interviews (with written participant consent) will be recommended.

Healthy normal participants will be recruited in order to demonstrate that these translated versions of the assessments result in similar observations independent of the language used for the study.

OUTCOMES: There will be several main outcomes from this sub-study. Importantly, these the preliminary data will inform power calculations for subsequent interventional trials. In addition, it will provide data to understand more fully the nature and course of frontal-type behaviours in HD. These data will help identify whether scales are sensitive in HD and at which stages.

The outcome of this sub-study will guide the suitability of these existing measures of frontal behaviours, in particular apathy and irritability, as clinical outcome tools for use in interventional trials in particular open-label efficacy trials.

It will also be important to combine the items included in all of the rating scales and look at the psychometric properties. This would inform about whether each item contributes

unique extra value compared to the other items. It would also be important to explore how each independent item performs relative to others in terms of Item Response Theory methods (IRT).

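### Frontal-behaviours sub-study (10.1.4): the stage quotas sum to 125 per country and 375 overall, not the stated 100 and 300

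*Protocol*

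**What the plan says.** All the figures stand in the methodological approach of Protocol section 10.1.4.

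- Countries: "The first phase will coordinate study sites across three countries".
- Overall size: "An estimated 300 participants recruited from different stages of the disease will be enrolled into the study".
- Size and composition per country: "100 participants in total per country; 50 Pre-HD, 25 Stage I, 25 Stage II and 25 Stage III".

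The study population of the same section is "Confirmed HD gene mutation carriers (Pre-HD, Stages I to III), aged 18 years and older", so all four quota groups are in scope. Healthy participants are mentioned separately ("Healthy normal participants will be recruited in order to demonstrate that these translated versions of the assessments result in similar observations"), without a number and outside the quota list.

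The same outline gives about 170 participants for test-retest reliability and 25 per language area for inter-rater reliability. No other section gives another total for this sub-study or explains the quotas.

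**The concern.** A total and the list of its parts stand in one parenthesis, and the parts do not sum to the total. A country team cannot fill every stage quota and also stay within the stated total.

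Two things are left undefined: how many people the first phase should enrol, and in what mix of disease stages. The mix matters because the outline expects the data to show at which stages the scales are sensitive and to inform power calculations for later trials. The number per stage affects how precisely either can be done.

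**Working it through.** **Inputs**, all from section 10.1.4: 3 countries; 300 overall; 100 per country; quotas 50, 25, 25 and 25.

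**The plan's own totals.** 3 × 100 = 300. The two stated totals agree with each other.

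**The quotas.**
- Per country: 50 + 25 + 25 + 25 = 125, against 100 stated. Difference 25.
- Overall: 3 × 125 = 375, against 300 stated. Difference 75, which is 75/375 = 20% of the quota sum, or 75/300 = 25% above the stated total.

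**Other readings tried.**
- Quotas as whole-study numbers: 125, which matches neither 100 nor 300.
- Pre-HD outside the total: 25 + 25 + 25 = 75 per country and 225 overall. No match, and Pre-HD is in the defined study population.
- Healthy participants counted in the total: they have no stated number, and adding them would widen the gap.
- Dropout: 125 recruited leaves 100 at a loss of 1 − 100/125 = 20%. The outline states no dropout allowance and calls the 100 a total.

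**Which figure slipped.** Several single slips would explain the text. With totals of 125 and 375 the quotas stand. With Pre-HD at 25 instead of 50, the sum is 4 × 25 = 100. With one group of 25 too many, it is 50 + 25 + 25 = 100, although the study population names all three manifest stages. The arithmetic does not choose between these.

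**Effect on precision.** Assume that the standard error of a stage-specific estimate varies as 1/√n with the within-stage standard deviation unchanged. The reference is the listed quotas.

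| Resolution (per country) | Pre-HD | Each manifest stage | Manifest-stage standard error |
|---|---|---|---|
| Quotas kept, total 125 | 50 | 25 | √(25/25) = 1.00 |
| 25/25/25/25, total 100 | 25 | 25 | √(25/25) = 1.00 |
| 40/20/20/20, total 100 | 40 | 20 | √(25/20) = 1.118, about 12% larger |
| Stop at 100 after Pre-HD fills | 50 | (100 − 50)/3 = 16.7 | √(25/16.7) = 1.22, about 22% larger |

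The last row also assumes that the remaining 50 places are shared equally. Over three countries it gives 50 per manifest stage instead of 75, and √(75/50) = 1.22 again. In the second row the reduction falls on Pre-HD, which halves from 50 to 25. The Pre-HD share is 50/125 = 40% in the first row, 25% in the second, 40% in the third and 50% in the fourth.

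**The case against.** The strongest reply concerns weight, since the sum itself is not in dispute. The figures sit in an appendix that summarises sub-studies. Section 5.4.7 says that each sub-study will have its own protocol and data analysis plan, and section 6.1 leaves sample size or power to each project proposal. The 300 is labelled an estimate and covers a first phase only. No hypothesis test, alpha or power is attached to it. The reliability components have their own numbers, which fit under either total. The main registry has open-ended enrolment and does not depend on this figure.

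All of that stands, and it limits the consequence. It does not remove the contradiction. The word for an estimate qualifies the 300; it cannot make a list that sums to 125 agree with a total of 100 in the same parenthesis. Under section 5.4.7, sub-study protocols also go to ethical review together with the main protocol, so the figures should agree now. Section 10.1.9 shows that an outline can be consistent: its four groups of 20 do sum to the 80 stated.

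A reader might infer more: that recruitment will stop at 100, that the manifest stages will be left short, and that stage-specific estimates will lose about 22% in precision. The documents do not support this. The 100 is a figure per country, not per site, and the outline gives neither a stopping rule nor an order in which the groups fill. The 22% needs both, and it disappears under two of the natural corrections. A reader might also infer that 375 is the true target. The document does not establish that either.

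**Conclusion.** The inconsistency is real: the quotas give 125 per country and 375 overall, against 100 and an estimated 300 stated. The 125 is plain addition. The 375 also rests on reading the quotas as per country, which the parenthesis supports; read as whole-study numbers they still fail.

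The effect is limited to this sub-study's recruitment target and stage mix. For the manifest stages, the rise in standard error runs from nothing, through about 12%, to about 22% in a hypothetical worst case, under the 1/√n assumption. The main cohort is not affected. As written, the text should not go forward into the sub-study protocol.

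**What to change.** The sponsor should say which figure is meant and state one consistent set in section 10.1.4:

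- keep the quotas and restate the totals as 125 per country and 375 overall; or
- keep 100 and 300 and change the quotas to sum to 100 per country, for example 25 in each of the four groups.

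The chosen set should then be carried into the sub-study protocol. The cost is a one-line correction. Keeping 300 adds no participants to the stated total; adopting 375 adds 75, each with the sub-study's assessment time for patient, companion and rater.

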### **10.1.5 Linguistic abilities**

**BACKGROUND:** HD has several typical cognitive deficits, including executive dysfunction (poor planning and organizational behaviours) and memory (impaired free recall of items). There have also been reports of language disorders in the disease, which assume a typically 'frontal' phenotype (poor verbal fluency and impaired syntactic abilities), possibly reflecting the fronto-striatal pathology associated with the disease. However, conflicting evidence from the few studies that have investigated this area make it unable to determine whether the impact of the subcortical damage caused by HD is related to dysfunction in language processing. Using more specific and sensitive tools than those classically used in aphasia evaluation, HD patients show impairments in language processing and more specifically in syntactic processing (3).

**AIM:** To demonstrate that syntactic assessment is a useful tool for longitudinal follow-up in HD and thus might be helpful in therapeutic trials. It may also discriminate between premanifest HD and controls.

**STUDY POPULATION:** HD gene mutation carriers, Pre-HD and early HD (Stage I).

**ASSESSMENT:** Sentence-Picture Matching Task (SPMT): 42 sentences

**ASSESSMENT DURATION:** 10 minutes

**METHODOLOGICAL APPROACH:** This study is designed to achieve the following objectives: to obtain clinical data on a sample of early HD patients and control participants and to characterize the nature of language impairment in these samples of HD patients.

The SPMT will be administered to 20 Pre-HD participants (Total Motor Score,  $\leq 5$ ), 20 early stage HD participants (Stage I, TFC 10-13) and 30 control participants (matched for age and education to HD groups) from each country participating in the study.

Longitudinal data will be collected following a one year interval, not more than two months apart from a full Enroll-HD evaluation to be able to extract the clinical characteristics of the patients.

OUTCOMES: Syntactic abilities using the SPMT in this population sample will be explored using ANOVAs with SPMT accuracy as the dependent variable and as independent variables: group (HD Stage I, Pre-HD and controls) as a between-subjects factor and canonicity (canonical and non-canonical sentences) and plausibility (plausible vs. non plausible) as within-subject factors. In addition, SPMT accuracy scores will be correlated with other scales assessing the evolution of the disease and the demographic characteristics (as covariates).

### **10.1.6 Validation of the Montreal Cognitive Assessment (MoCA) General Cognitive Impairment**

BACKGROUND: As clinical trials to assess the efficacy of so called ‘cognitive enhancers’ are likely to be developed in the near future, it is worthwhile to validate the Montreal Cognitive Assessment (MoCA) as a tool for detecting ‘global’ cognitive change in HD that might not be evident in scores on those tasks currently included in the Enroll-HD protocol.

AIM: To investigate cross-sectional and longitudinal sensitivity of the MoCA to cognitive change in different stages of HD, including premanifest HD. Additionally the test-retest reliability will be investigated. The inclusion of non-HD gene carriers will permit the collection of normative data on this task.

STUDY POPULATION: Confirmed HD mutation carriers of all stages of the disease including premanifest-HD.

ASSESSMENT: MoCA, rater administrated.

ASSESSMENT DURATION: 5-10 minutes

METHODOLOGICAL APPROACH: In order to investigate the cross sectional and longitudinal sensitivity of the MoCA, as well as the test re-test reliability participants will be stratified according to six groups; gene-negative controls, Pre-HD individuals (TFC =13, TMS ≤ 5), and individuals in the early (Stage I), mild (Stage II), moderate (Stage III) and severe (Stage IV) stages of HD.

Population sample size: 50 non-mutation gene carriers, 100 pre- HD gene carriers, 100 HD Stage I, 50 HD Stages II and III, and 25 HD Stage IV.

The study will follow semi-randomised design. Study sites should commit to pre-specified “packages” for data collection. Two packages are offered: a) to include four

participants in Stage I, two participants in each Stage II and III, and one participant in Stage IV; b) includes one control non-gene carrier and two pre-motor manifest HD gene carriers.

Once these data are collected, they will be used to guide towards further refined aims, such additional stratification according to demographic variables as age and education, and language.

To determine the longitudinal sensitivity of this measure, the same procedure will be followed, where participants will be followed up one year later.

The test re-test reliability of the MoCA will be determined following the same procedure for a smaller number of individuals in each stage, after an interval of one month. This will require 40 Stage I, 20 Stage II, 20 Stage III and 10 Stage IV participants. Primary outcomes will involve indices of sensitivity (0.9) – specificity (0.85) of the MoCA within the HD population (stages I–IV and pre-motor manifest HD gene carriers) and healthy control participants. Additionally re-test reliability measures will be obtained within these population samples.

**OUTCOMES:** This study will seek to examine the use of the MoCA as a tool for detecting and tracking ‘global’ cognitive change in HD that might not be evident in scores on those tasks currently included in the Enroll-HD protocol.

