For the purposes of the Enroll-HD study the terminology 'manifest/motor-manifest' vs 'pre-(motor)-manifest' will be used to describe the population of HD expansion mutation carriers. It is acknowledged that recent data from PREDICT-HD and TRACK-HD provide strong evidence for the concept of a prodromal stage of HD with measurable abnormalities in several domains including magnetic resonance imaging and quantitative motor tests years before a conventional HD diagnosis based on the emergence of diagnostic motor signs. However, the same studies support the concept of a stage in the life of HD expansion mutation carriers during which no features distinguishing mutation carriers from non-mutation carriers can be identified. In addition, it is acknowledged that dividing a continuum of disease manifestations into qualitatively distinct stages (pre-motor-manifest vs. motor-manifest) is somewhat arbitrary and that the criteria defining such stages are a matter of ongoing debates. However, given the need to communicate that carriers of the HD expansion mutation irrespective of the presence or absence of clinical features as well as people at risk are invited to participate in Enroll-HD, given the wide use of the pre-manifest/manifest terminology, and given the increased use of stage-dependent assessment tools in the current version of the protocol this terminology is employed purely for practical reasons.

Participant status will be captured in the study database using 2 variables: 1) Investigator Determined Status: this will be based on clinical signs and symptoms and genotyping performed as part of medical care and will be updated at every visit and 2) Research Genotyping Status: this will be based on genotyping conducted as part of Enroll-HD study procedures. Based on research genotyping, participants will be reclassified under this variable from Genotype Unknown to 'Carriers' or 'Controls'. Investigators and participants will be blinded to this reclassification.

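### MoCA sub-study: sensitivity 0.9 is stated for a case group that includes pre-manifest carriers, the site packages can separate manifest cases from controls, and the one-month retest leaves out two of the six groups

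*Protocol*

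**What the plan says.** All of this is in Protocol section 10.1.6 unless another section is named.

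- **Aim.** The sub-study examines how sensitive the MoCA is to cognitive change across disease stages, premanifest HD included, and its retest reliability. The stated rationale is to find global change that the tasks already in the Enroll-HD protocol could miss.
- **Primary outcome.** This is given as "indices of sensitivity (0.9) – specificity (0.85) of the MoCA within the HD population (stages I–IV and pre-motor manifest HD gene carriers", with healthy controls completing the list. The outline does not say whether this is one index or one per stage.
- **Group sizes.** "50 non-mutation gene carriers, 100 pre- HD gene carriers, 100 HD Stage I, 50 HD Stages II and III, and 25 HD Stage IV". Participants are stratified into six groups: controls, pre-HD (TFC 13, TMS at most 5) and Stages I to IV.
- **Packages.** Sites commit to packages. Package (a) is four Stage I, two Stage II, two Stage III and one Stage IV. The other package "b) includes one control non-gene carrier and two pre-motor manifest HD gene carriers".
- **Retest at one month.** "This will require 40 Stage I, 20 Stage II, 20 Stage III and 10 Stage IV participants". The same paragraph ends by announcing retest measures in the samples it has just listed, which include pre-manifest carriers and controls.
- **Carriers before motor onset.** Section 4.2.1 accepts that there is "a stage in the life of HD expansion mutation carriers during which no features distinguishing mutation carriers from non-mutation carriers can be identified". It also cites strong evidence for a prodromal stage with measurable abnormalities. Section 10.1.1 describes the changes in carriers with TMS at most 5 as very slight.

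**The concern.** Three choices in the outline work against what the sub-study wants to show.

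1. **Case group.** The stated sensitivity covers manifest patients and pre-manifest carriers together, although the test is meant to detect cognitive change and not carrier status. Carriers with no detectable cognitive change count as misses. A pooled value then depends heavily on how many pre-HD participants were recruited, and a test that works well in manifest HD could show a sensitivity well below 0.9.
2. **Packages.** Manifest patients and controls arrive in different packages. If some sites take only (a) and others only (b), the comparison of manifest HD with controls is also a comparison of sites, raters and languages, for a test that a rater administers in several languages.
3. **Retest.** Reliability is announced for groups that receive no retest places, so one-month reliability in pre-HD and controls cannot be estimated from the plan as written.

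**Working it through.** **Inputs from section 10.1.6:** specificity 0.85, so 15% of controls test positive; stated sensitivity 0.9; the group sizes, package contents and retest numbers above. The document gives no MoCA cut-off, no pre-HD positive rate, and no power or precision basis for 0.9 and 0.85.

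**Step 1: reproduce the group sizes.**
- 25 copies of package (a): 25 × (4, 2, 2, 1) = 100 / 50 / 50 / 25 for Stages I / II / III / IV, or 225 manifest.
- 50 copies of package (b): 50 × (1, 2) = 50 controls and 100 pre-HD.
- Total 225 + 100 + 50 = 375.

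The packages fit the reading of 50 in each of Stages II and III. As the sentence also allows 50 combined (175 manifest), both are carried forward. The pre-HD share of carriers is 100/325 = 31%, or 100/275 = 36%.

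**Step 2: ceiling on pooled sensitivity.** With manifest sensitivity S and pre-HD positive rate q,

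pooled sensitivity = (n_manifest × S + 100 × q) / (n_manifest + 100).

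Assume pre-HD score like controls (q = 0.15) and every manifest patient is detected (S = 1):
- (225 + 15)/325 = 0.738
- combined reading: (175 + 15)/275 = 0.691

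With S = 0.90 the first becomes (202.5 + 15)/325 = 0.669.

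**Step 3: pre-HD positive rate needed for 0.90.**
- S = 1: (0.9 × 325 − 225)/100 = 0.675; combined reading (0.9 × 275 − 175)/100 = 0.725
- S = 0.95: (292.5 − 213.75)/100 = 0.788
- S = 0.90: (292.5 − 202.5)/100 = 0.90

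Under equal-variance normal scores, the shift needed between pre-HD and controls is z(q) + z(0.85). For q = 0.675 it is 0.454 + 1.036 = 1.49 SD; for 0.725, 1.63 SD; for 0.90, 2.32 SD. The last figure is also what pre-HD would need if 0.9 applies to each stage separately.

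**Step 4: range over the unknown.** Ceilings (S = 1) for assumed pre-HD shifts:

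| Shift (SD) | Pre-HD positive | Ceiling, 325 cases | Ceiling, 275 cases |
|---|---|---|---|
| 0 | 0.150 | 0.738 | 0.691 |
| 0.2 | 0.201 | 0.754 | 0.710 |
| 0.5 | 0.296 | 0.783 | 0.744 |
| 0.8 | 0.407 | 0.817 | 0.784 |
| 1.0 | 0.485 | 0.842 | 0.813 |
| 1.5 | 0.679 | 0.901 | 0.883 |

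**Step 5: packages.** All 225 manifest cases come from package (a), which has no controls. All 50 controls come from package (b), which has no manifest cases. The 100 pre-HD participants share package (b) with the controls. Stratification by age, education and language is mentioned only for after the data are in.

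**Step 6: retest.** 40 + 20 + 20 + 10 = 90 = 10 × (4 + 2 + 2 + 1). The retest sample is ten copies of package (a) and none of (b), so pre-HD and controls receive zero places.

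**The case against.** Several points on the other side are sound.

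- **Section 10.1 is a summary.** Each sub-study is to have its own protocol and analysis plan (sections 5.4.7 and 6.2), where cut-off, reference standard and analysis may be settled. That stands for what the outline leaves out. It does not cover the case group, group sizes, packages and retest numbers, which the outline states. For the same reason, the lack of any described random step in a design called semi-randomised is not pressed here.
- **Pooling is not explicit.** The text speaks of indices in the plural, and the aim refers to different stages, so reporting by stage may be intended. This stands, and the ceiling is therefore conditional. But if 0.9 is meant stage by stage, pre-HD alone needs 90% positive.
- **A reader might infer that 0.9 cannot be reached, or that the test would formally fail.** The documents do not support either. They give no pre-HD positive rate, section 4.2.1 points to measurable prodromal abnormalities as well as to an indistinguishable stage, and 0.9 and 0.85 are nowhere called pass marks.
- **A reader might infer that cases and controls will come from different sites.** The outline permits this but does not require it, and it applies to manifest cases only. The training and certification in section 5.1 should reduce rater differences. No size can be put on a site effect from the documents.
- **A reader might infer that one-year change has no practice-effect reference.** That fails: the one-year follow-up repeats the same procedure, which includes controls and pre-HD.
- **The retest sentence speaks of each stage,** which could mean Stages I–IV only. The stratification sentence and the closing sentence of the retest paragraph nevertheless extend retest reliability to the other two groups.

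**Conclusion.** The point holds in a limited, partly conditional form.

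- **Retest:** an internal mismatch that needs no assumption. Six groups are included in the claim; four receive places.
- **Case group:** if one pooled index is meant and pre-HD score like controls, sensitivity is capped at 0.74 (0.69 on the combined reading). Reaching 0.90 needs at least 67.5% (72.5%) of pre-HD positive while 15% of controls are, and that minimum already supposes perfect detection in manifest HD. This is arithmetically possible, but it sits badly with the slight changes that section 10.1.1 describes at TMS at most 5. For shifts up to 1 SD the ceiling stays at or below 0.84.
- **Packages:** manifest cases and controls can come from different sites, raters and languages. This is an avoidable risk of unknown size.

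Severity is moderate. One optional sub-study is affected, and no objective of the main registry depends on it.

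**What to change.** 1. **Sensitivity by stage.** Report it separately for Stages I, II, III and IV and for pre-HD, and attach the 0.9 figure to manifest HD only. With 225 manifest cases, an observed 0.90 has a 95% Wilson interval of about 0.854 to 0.933. Specificity 0.85 on 50 controls has about 0.726 to 0.924, whichever case definition is used. State whether the 50 for Stages II and III is each or combined.
2. **Reference standard.** Do not define impairment by the core cognitive battery. The aim is to find change that battery may miss, so such findings would be scored as false positives.
3. **Packages.** Where feasible, have each site take them in a ratio of one (a) to two (b). One unit is 9 + 2 × 3 = 15 people covering all six groups, and 25 × 15 = 375, unchanged. Where this is not feasible, account for site and language in the comparison of manifest cases with controls.
4. **Retest.** Move part of the 90 places to pre-HD and controls, for example 20 / 20 / 20 / 10 for Stages I–IV with 10 pre-HD and 10 controls (total 90). Otherwise restrict the retest claim to Stages I–IV.

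**Cost.** Wording changes in one sub-study; no added participants or tests. A site would commit to 15 people instead of 9 or 3. Retest precision in Stage I falls: going from 40 to 20 widens its standard error by roughly √(40/20) = 1.41. Ten places in each new group give only a rough reliability estimate.
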